Aim 2. Aim 2 is to provide a preliminary test of the response to the three memory interventions. At baseline, TBI survivors will be evaluated for memory function in each of these three memory component processes using established neuropsychometric methods. Their experimental treatment allocation will be to the treatment targeting their most impaired memory component. In addition, each subject will serve as his/her own control, by engaging in a treatment targeted to another memory component ('mismatched' group).

Hypothesis A. The matched vs. mismatched group will show differential improvement in memory component function, with the former group benefitting to a significantly greater degree. (Primary measures: Memory component performance, encoding, consolidation, retrieval; secondary: cognitive function and quality of life).

Aim 3. Aim 3 is to establish links between the behavioral taxonomy of the three memory components and differences in brain structure and function documented with diffusion tensor imaging and functional connectivity analysis. This is a key first step in establishing brain-based metrics of neuroplastic change after memory therapy in our research program.

Objective 3.1. Identify specific and unique imaging signatures that distinguish patients with deficits in encoding, consolidation, and retrieval, respectively. Primary measures: structural measures of morphometry and white matter integrity (FA) and functional connectivity (cross correlation and total interdependence) in identified brain networks damaged in TBI.

Clinical Implications. This research has the potential to devise a method to match specific

subcomponents of memory impairment to specifically targeted memory interventions, thus maximizing recovery of memory and function. The results of this investigation will be used to refine the interventions, to evaluate cognitive and functional endpoints, and to power a larger clinical trial that will yield data enabling clinicians to match TBI patients to effective treatments based on their individual profile of memory dysfunction.

6. Research Plan:

6.1. Study Design. The proposed research will be conducted in three phases: Intervention Development, Patient Characterization and Classification, and Initial Testing of Treatment Efficacy.

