6.3.2.2. Classifying Participants into Process-Specific Groups

We aim to identify M-STBI patients whose injuries produce primary deficits in encoding/acquisition, consolidation/retention, or retrieval. While we expect that many patients may have some problems in more than one domain, many studies have concluded that memory problems after M-STBI are *primarily* rooted in one of these domains at the individual level^{5-7,56,57}. Three studies^{4,7,58} report distinct deficit patterns attributable to encoding, consolidation, and retrieval deficits using the CVLT⁵⁹. Crosson et al⁷ found that encoding deficits were marked by a high false positive (FP) rate and reduced hits on recognition, while consolidation deficits were marked by lower hit rates and lower FP (also see⁵⁸). Curtiss et al⁵⁶, using hierarchical clustering of CVLT and WMS-R variables, found three memory-impaired groups corresponding to acquisition/encoding, retention, and retrieval deficits. Millis and Ricker⁴ used Delis⁵⁹ six-factor solution of CVLT performance variance to identify patterns of verbal learning deficit after moderate-severe TBI. They found 4 identifiable clusters: a Disorganized type (n = 22; encoding deficit) who exhibited a haphazard learning style, elevated FP rate, reduced discriminability on recognition testing and increased susceptibility to proactive interference, an Active type (n = 15; retrieval deficit) who showed good semantic encoding, good acquisition rate, and disproportionate improvement on recognition (discriminability), a Passive type (n = 11; consolidation deficit) whose recall showed prominent serial position effects and rapid forgetting, and a Deficient type (n = 13; encoding deficit) who showed slow rate of learning, recency effects in free recall, and an excessively high FP rate on recognition. These results were subsequently replicated and extended³. We will use this classification scheme, summarized in Table 2. Deficient and Disorganized groups will be collapsed, as both suffer from encoding deficits. Characteristics of each class (encoding, consolidation, and retrieval) will be combined in multivariate fashion, creating a composite score. Participants will be assigned to the group corresponding to the most impaired composite score. We will also investigate other algorithms for classifying patients, with the goal of deriving the most accurate and stable method.

Table 2. Scheme for Classifying TBI patients into deficit categories.

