Deficit	Encoding Deficit	Consolidation Deficit	Retrieval Deficit
Millis/Ricker/Deshpande Grouping	Disorganized (I) Deficient (IV)	Passive (III)	Active (II)
CVLT Factor Score Comparisons	Serial cluster <III, =II Primacy <III, =II Slope < II, =III FR Intrus =II, III List B v. A <II, =III	Serial cluster >I,IV,=III Primacy II Slope =I,IV, <II FR Intrus <IV, =II List B v. A =I,III,IV	Serial cluster =I, >III Primacy <III, =I,IV Slope >I,III,IV FR Intrus <III,=I,IV List B v. A >I, =III,IV
CVLT Performance Features	False pos >II,III Recency >II,III Recog Discrim <II,III	False pos <I,II,IV Recency <I Recog Discrim <I Semantic cluster <II SDFR v. Trial 5 >II	Semantic cluster >III,IV SDFR v. Trial 5 <III,IV FR Consist >I,IV Total (1-5) >I,IV List B >I,IV

6.3.2.3. Structural/Functional Neuroimaging. A long-term goal of our research is to provide evidence of neuroplastic changes after memory interventions by documenting treatment-related change in structural integrity and functional brain connectivity. In this study, we will collect pre-treatment MRI data to provide brain-based biomarkers of our 3-group classification. Participants will be offered \$50 for participation in each of two MRI acquisitions, once before treatment, and again 1 month post-treatemtn.

6.3.2.3.1. Acquisition Protocol. The MRI acquisition protocol is outlined in Table 3.

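### Patients are assigned by their most impaired composite, but Table 2's Retrieval column lists mainly strengths, the scoring direction is unstated, and several Table 2 rows conflict as printed

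*Protocol*

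**What the plan says.** Protocol Section 6.3.2.2 adopts a four-type CVLT classification summarised in Table 2. The Encoding column is headed "Disorganized (I) Deficient (IV"), Consolidation is the Passive type (III) and Retrieval is the Active type (II). On scoring it says: "Characteristics of each class (encoding, consolidation, and retrieval) will be combined in multivariate fashion, creating a composite score". The assignment rule follows: "Participants will be assigned to the group corresponding to the most impaired composite score". Aim 2 uses the same idea: "Their experimental treatment allocation will be to the treatment targeting their most impaired memory component". No sign, weight, norm or cut-off is given for any index.

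The text describes the types in words. Active patients "showed good semantic encoding, good acquisition rate, and disproportionate improvement on recognition (discriminability"). Disorganized patients (I) had "reduced discriminability on recognition testing and increased susceptibility to proactive interference". Passive patients are those "whose recall showed prominent serial position effects and rapid forgetting". The section closes: "We will also investigate other algorithms for classifying patients, with the goal of deriving the most accurate and stable method".

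SAP Section 2.6 refers to a Section 2.3.2 for the classification procedure, which is not in the text available for this review. It also uses all three composites as exploratory predictors of response.

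**The concern.** A most-impaired rule needs each composite to fall, or rise, as that deficit worsens. Most entries in the Retrieval column describe what the Active type does well, so a low score built from them looks more like an encoding problem than a retrieval problem. The one feature in the text that points to retrieval failure, recognition improving out of proportion to recall, is not in that column. Several Table 2 rows also cannot all be true as printed, so a programmer could not turn the table into scoring syntax without making choices.

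The label decides which treatment counts as matched in Hypothesis A, which Table 4 orders a patient can receive, and the groups compared on imaging in Aim 3. With four patients per group, one wrong label is a quarter of a group.

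**Working it through.** The plan gives no figure to reproduce here. The check has four parts.

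**1. Direction of the Table 2 entries.** Each printed comparison of a column's own type with another type is counted as better/worse/tied. Encoding entries are counted once as printed, and comparisons of a type with itself are left out. Serial cluster, primacy and recency are treated as style and not counted. Assumed directions:
- Low List B v. A is read as the proactive interference that the text gives to type I.
- SDFR v. Trial 5 is read as loss, because the higher value belongs to type III, which the text describes as forgetting rapidly.

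| Index | Encoding (I, IV) | Consolidation (III) | Retrieval (II) |
|---|---|---|---|
| Slope | 0/1/1 | 0/1/2 | 3/0/0 |
| FR intrusions | 0/0/2 | 1/0/1 | 1/0/2 |
| List B v. A | 0/1/1 | 0/0/2 | 1/0/2 |
| False positives | 0/2/0 | 3/0/0 | none |
| Recognition discriminability | 0/2/0 | 0/1/0 | none |
| Semantic cluster | none | 0/1/0 | 2/0/0 |
| SDFR v. Trial 5 | none | 0/1/0 | 2/0/0 |
| FR consistency | none | none | 2/0/0 |
| Total 1-5 | none | none | 2/0/0 |
| List B | none | none | 2/0/0 |
| **Sum** | **0/6/4** | **4/4/5** | **15/0/4** |

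If SDFR v. Trial 5 is scored as retention, Retrieval becomes 13/2/4 and Consolidation 5/3/5. Either way one rule meets three columns of different character.

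The direct comparison of type II with type IV, on the eight directional indices in the Retrieval column, gives 6 better, 2 tied and 0 worse (loss-scored), or 5, 2 and 1 (retention-scored). On a performance reading, an encoding-type patient would therefore usually look more impaired on the Retrieval composite than an Active-type patient.

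**2. The recognition marker.** None of the 10 Retrieval entries concerns recognition. Type II appears only as a comparator for discriminability in the Encoding column, which is not a contrast between recognition and recall.

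**3. Consistency of the 13 Table 2 measures.** Every printed relation was written out for types I to IV.

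| Measure | Conflict as printed | Holds when |
|---|---|---|
| Primacy | III is both below and above II in one Consolidation cell; also I<III (Encoding) against III<I (Consolidation) | II-III on every reading of the Encoding heading; I-III if Encoding covers I |
| FR intrusions | II<III (Retrieval) against III=II (Consolidation); also III<IV against IV=III | II-III unless the cells come from different samples; III-IV if Encoding covers IV |
| Recognition discriminability | I<III (Encoding) against III<I (Consolidation) | Encoding covers I, as its heading says |
| List B v. A | IV<II (Encoding) against II=IV (Retrieval) | the Encoding entry covers IV |
| Serial cluster | I<III and III<II, yet I=II | = means equality |

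Type III is also compared with itself under serial cluster and List B v. A. The other eight measures are consistent.

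Reading = as not significantly different does not easily rescue serial cluster. Assume the comparisons come from the clusters in the text (n = 22, 15 and 11 for I, II and III) with a common SD. Standard errors in SD units are:
- I-III: √(1/22+1/11) = 0.369
- II-III: √(1/15+1/11) = 0.397
- I-II: √(1/22+1/15) = 0.335

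Two significant steps put the I-II gap at no less than (0.369+0.397)/0.335 = 2.29 times its own threshold.

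**4. Cost of one wrong label, from any cause.** Assume one true class per patient, a benefit d from the truly matching treatment, and no difference between the other two. In each set of four Table 4 orders, two contain the truly matching treatment as the mismatched one (contrast −d) and two do not contain it (contrast 0). The expected contrast is (−d−d+0+0)/4 = −0.5d instead of +d. With one wrong label among four, the group mean is (3d−0.5d)/4 = 0.625d on average.

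**The case against.** The strongest reply is that the composites were never meant as performance scores. Section 6.3.2.2 treats good performance as a class marker in its own descriptions, and it speaks of combining the characteristics of each class. Likeness to a profile is a natural reading, and on it the rule works. This stands, and it limits the point. What remains is that the text does not say so, and that both the rule and Aim 2 use the language of impairment.

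Table 2 is called a summary, so a feature missing from it may still enter the composite. That is possible, but the table is the only itemised list of inputs.

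The table conflicts may be slips. Reversing one sign would cure primacy, recognition discriminability or serial cluster. Applying one Encoding entry to type I alone would remove the List B v. A clash between II and IV. The grouping row names both the first cluster study and its replication, so the FR intrusions cells could come from different samples. All of this is fair, and it is why the table needs checking against its source. It does not make the printed table usable.

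The sentence on other algorithms says they will also be investigated, which reads most naturally as additional work. It does not show that the assignment rule is open. It only leaves unsaid that the stated rule governs Phase 3.

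**Conclusion.** The point holds in a limited form and should be fixed. The assignment rule and the Retrieval column fit together only if the composites score likeness to a profile, and the text available does not say that they do. The column is mainly strengths under either SDFR direction (15/0/4 or 13/2/4) and omits the text's recognition marker. Primacy contradicts itself within one cell, and type III is compared with itself twice. Four further measures conflict under the conditions tabulated above.

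A reader might infer more, and the documents do not support it:
- That retrieval patients will be misclassified. This follows only as a tendency, and only if low composites mean impairment. No rate can be derived.
- That the Active type is never worse on any entry, or that type IV looks more retrieval-impaired under any positive weights. Both depend on SDFR v. Trial 5 being loss-scored, which the protocol does not state. The second also leaves out serial cluster and primacy.
- That all five measures conflict on every reading. Only primacy contradicts itself inside a single cell.

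The cost of a wrong label in part 4 is general to the design and is not evidence that this rule produces wrong labels. The SAP's use of all three composites reduces reliance on one label but inherits the same scoring.

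**What to change.** - Replace the most-impaired wording with a signed rule: a higher composite always means closer to that deficit profile, and the patient goes to the highest. Align Aim 2 with it.
- State the sign of each CVLT-II index, including SDFR v. Trial 5.
- Add a contrast of recognition against free recall to the Retrieval composite, as the text's description of the Active type implies. Delayed free recall is one possible comparator; it is a suggestion here and is not named in the protocol.
- Check primacy, FR intrusions, recognition discriminability, List B v. A, serial cluster and the two self-comparisons against the source table and reconcile them. For primacy, begin with the Consolidation cell, since the other two columns put type III above the rest. Say which Encoding entries apply to I, to IV or to both.
- Confirm that each reference profile scores highest on its own composite.
- Use this one rule for Phase 3 assignment and keep other algorithms for sensitivity analysis. If patients are already assigned, rescore their stored data and report both labels.

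The cost is small: protocol wording and scoring syntax for a test that is already part of the Phase 2 battery. The downside is that the Retrieval and Consolidation composites may overlap through recall, so their correlation should be reported.

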6.4. Phase 3: Initial Testing of Treatment Efficacy

6.4.1. Overview. In this phase, appropriately classified patients will be assigned to participate in two memory interventions, one matched to their primary deficit, the other

mismatched, in counterbalanced order. The overall framework is outlined in Table 4; shaded cells are “matched” conditions.

6.4.2. Design. The overall approach is a ***multiple-subject Alternating Treatment Design***, effective for determining the relative efficacy of two treatments in a single individual⁸⁰. One participant will be assigned to each treatment order in Table 4, such that 4 patients per classification group (12 total) will participate. Each participant will receive 1 matched and 1

Table 4. Treatment Schedule

Memory Deficit	Treatment Strategy/Target			Treatment Orders (one matched, one mismatched; counterbalanced)
	Memory Strategy Training (1)	Errorless Learning (2)	Retrieval Practice (3)	
Encoding	+/+	+/-	+/-	12, 13, 21, 31
Consolidation	-/+	+//	+/-	21, 23, 12, 32
Retrieval	-/+	-/+	+//	31, 32, 13, 23

mismatched treatment, in counterbalanced order. Therapists will be blinded to patient classification.

Although this design is subject to multiple-treatment interference⁸¹ (the notion that the effects of each of the interventions might be affected by the presence of another intervention), such

[figure not shown]

Figure 1. Hypothetical data of two patients, one with encoding deficit (blue), the other with retrieval deficit (red).

carryover effects are typically small and counterbalancing the order of treatments should further reduce treatment carryover⁸⁰. The design permits comparison of treatment effects in conditions in which a treatment is given first vs. second. New methods for calculating treatment effect size and possible confounding factors are available⁸²⁻⁸⁵. ***It is hypothesized that greater gains in memory will be seen in matched, as compared to unmatched, treatments.*** This is illustrated by hypothetical data presented in Figure 1, where a patient with encoding deficits (blue) benefits more [greater elevation and slope] from memory strategy training than from retrieval practice, while the opposite pattern is seen

in the patient with retrieval deficits (red). Each treatment will be conducted twice weekly for 3 weeks (6 sessions). Thus, each participant's involvement in actual treatment will span 6 weeks (2 treatments). Participants will be offered \$20/session for participation as inconvenience cost and to help them defray travel expenses. We will conduct a 1-month follow-up at which time performance on proximal outcomes (performance on VPA and FNP tasks) and secondary outcomes (see below) will be evaluated.

6.5. Secondary Outcome Measures

We will collect preliminary data on secondary outcome measures (Table 5) derived from the Interagency Traumatic Brain Injury Outcomes Workgroup recommendations⁸⁶. Measures will be collected before treatment, immediately after the conclusion of each treatment (during the last treatment session), and 1 month after treatment has concluded. The \$50 paid to the participant to undergo post-treatment MRI scanning will also cover the collection of 1-month post-treatment secondary outcome measures, since they will be collected on the same day.

Table 5. Secondary Outcome Measures

Domain	Purpose	Measure
Global Outcome	Summarize overall TBI impact	MPAI-4
Memory Impairment	Characterize memory deficits	RAVLT, BVMT-R, Everyday memory simulations from EON-MEM ^a
Social Role Participation	Evaluate involvement and participation in life situations	CHART-SF
Self-reported and general Quality of Life	Perceived satisfaction and well-being	SWLS, QUOLIBRI
Patient Reported Outcomes	Evaluate outcome from patient evaluation perspective	PROMIS ^b and Neuro-QOL ^c Item Banks

^aAddress/Phone Number, News Article, Face-Name Learning simulations; ^bApplied Cognition-Abilities, Applied Cognition-General Concerns; ^cExecutive Function, General Concerns

7. Possible Discomforts and Risks:

7.1 **Risks Associated with MRI:** Magnetic resonance imaging (MRI) is a procedure that allows doctors to look inside the body by using a scanner that sends out a strong magnetic field and radio waves. This procedure is used routinely for medical care and is very safe for most people, but you will be monitored during the entire MRI scan in case any problems occur. The risks of MRI are:

- The MRI scanner contains a very strong magnet. Therefore, you may not be able to have the MRI if you have any type of metal implanted in your body, for example, any pacing device (such as a heart pacer), any metal in your eyes, or certain types of heart valves or brain aneurysm clips. Someone will ask you questions about this before you have the MRI.
- There is not much room inside the MRI scanner. You may be uncomfortable if you do not like to be in closed spaces ("claustrophobia"). During the procedure, you will be able to talk with the MRI staff through a speaker system, and, in the event of an emergency, you can tell them to stop the scan.
- The MRI scanner produces a loud hammering noise, which has produced hearing loss in a very small number of patients. You will be given earplugs to reduce this risk.
- If you are a woman of childbearing potential, there may be unknown risks to the fetus. Therefore, before you can have the MRI, you must have a pregnancy test.

7.2 **Risks Associated with Memory/Cognitive Testing:** When undergoing memory and cognitive ability testing, there is the risk of fatigue and frustration while taking the tests. Our trained examiners attempt to provide frequent breaks and utilize techniques to minimize frustration.

7.3 **Risks Associated with Participation in the Memory Treatment Program:** There are no known risks associated with participating in the memory treatment program.

7.4 **Other Risks:** Other possible risks to you may include: Normal risk associated with travel to and from UF and VA facilities.

8. Possible Benefits:

Patients may or may not benefit from participating in this research study. This research tests the effectiveness of memory rehabilitation therapies for helping Veterans with TBI-related memory problems. Since we are testing these treatments, we do not know how effective they are. Each participant will be given at least two such therapies, which may bring some benefit in memory by teaching strategies for remembering new information. The patient may also gain a better understanding of the effects of brain injury on memory function.

Other nonparticipating patients may benefit from our increased understanding of patterns of memory difficulty after mild traumatic brain injury that might respond better to particular memory rehabilitation therapies. Once we understand these patterns, we can better match patients to effective treatments designed to alleviate memory dysfunction.

9. Conflict of Interest: None, other than the typical benefit the PI and Co-I's get from presenting or publishing research results.

10. Literature Cited

- 1 Bauer, R. M., Reckess, G. Z., Kumar, A. & Valenstein, E. Amnesic Disorders. In *Clinical Neuropsychology* (eds K.M. Heilman & E. Valenstein) 504-579 (Oxford University Press, 2012).
- 2 Rosenbaum, S. B. & Lipton, M. L. Embracing chaos: the scope and importance of clinical and pathological heterogeneity in mTBI. *Brain Imaging Behav* **6**, 255-282, doi:10.1007/s11682-012-9162-7 (2012).

## 2.6. Statistical Analysis Plan

The procedure for classifying participants into Encoding, Consolidation, and Retrieval groups is outlined in Section 2.3.2. It is recognized that, although patients will be classified according to their primary memory deficit, some may have relevant impairment in more than one domain. For this reason, each participant will be given a composite score for encoding, consolidation, and retrieval, and all three of these composite scores will be used in exploratory analyses of predictors of treatment response. Phase 2 neuropsychological scores (z-score transformed data using appropriate age- and education corrections) and neuroimaging data (NEW, FA, diffusivity measures, morphological volumes, TI from RS-fMRI for specific ROI pairs) will be analyzed using 1-way (Group: Encoding, Consolidation, Retrieval) ANOVAs followed by pairwise follow-ups with the Tukey HSD test. Dependent variables used to evaluate memory performance in Phase 3 are detailed in Section 2.2 above, and include session-wise percent correct data on VPA and FNP memory probes as well as post-treatment and 1-month follow-up probes. Data from Phase 3 will be analyzed by comparing effect sizes of matched and unmatched treatments at the individual subject level using methods described by Parker et al. These measures include (a) percentage of non-overlapping data points, (b) quantitative measures of improvement rate and difference level, and (c) Tau-U, a nonparametric measure of effect size that tests for differences in two treatments after trend adjustment. Additional measures will also be explored, including interrupted time-series/regression approaches and the last-day-of-treatment comparison approach. We will also evaluate the separate influence that severity of memory deficit has on treatment response (independent of patient grouping) by performing hierarchical linear regression in which severity is coded as average z-score on memory indices derived from phase 2, and patient grouping is dummy-coded.

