salience network (SN). The **DMN** consists of interconnected regions in the posterior cingulate cortex, medial and lateral parietal cortex, and medial prefrontal cortex, which show *deactivation* during active task conditions⁶⁷. The **TPN**, centered on connections between medial and dorsal regions of the frontal and parietal lobes, becomes more activated when the brain is presented with an attentionally demanding task⁶⁸; activity within this region during encoding is associated with accurate retrieval later on⁶⁹. The **SN**, comprised of dorsal anterior cingulate and the bilateral insula, responds to salient events and provides interaction between cortical, limbic, and subcortical structures essential for learning⁷⁰. M-STBI is associated with abnormalities in the DMN⁷¹⁻⁷⁴, TPN⁷³, and SN⁷⁵. It has been suggested⁷³ that TBI disrupts the normal segregation of

Table 3. MRI Protocol – UF AMRIS 3T Philips System; 32 Channel Head Coil
Total Scan Time = 43m 55s

Sequences	Purpose	Parameters
3D T1	Gray-white matter segmentation	176 continuous slices, voxel=1mm ³ , TR/TE=7.0/3.2ms, flip angle=8°, FOV=240x240mm, matrix=240x240x176mm, time: 4m 34s
3D FLAIR	Structural lesion identification, segmentation	180 continuous slices, voxel=1mm ³ , TR/TE=8000/338ms, IR=2400ms, flip angle=90°, FOV=240x240mm, matrix=240x240x180mm, time: 7m 12s
T2	Brain extraction	176 continuous slices, voxel=1mm ³ ; TR/TE=2500/363ms; FOV=240x240, flip angle=90°; matrix=240x240x165; time: 5m 27s
SWI	Micro-hemorrhage detection	Flow-compensated gradient echo; TR/TE1/ΔTE=59/8/6ms, FOV=240x192mm, flip angle=22°, matrix=240x192x170mm, voxel=1x1x2mm ³ , time = 5m 31s
HARDI	Fiber integrity, fiber modeling	74 continuous slices, 64 directions (1000s/mm ²), 6 directions (100/mm ²), voxel=2mm ³ , TR/TE=4840/86ms, flip angle=90°, FOV=224x224mm, matrix=224x224x140mm, time: 13m 1s
RS-BOLD	Resting state functional connectivity	36 slices, Single-shot EPI sequence, TR/TE=2500/30ms, flip angle=90°, FOV=252x252mm, matrix=72x72x36mm, slice thickness=3.5mm, voxel=3.5mm ³ , time: 8m 10s

the DMN and TPN through white matter damage to large corticortical pathways^{76,77} and through damage to pathways that link the SN with the DMN and TPN. Such abnormalities are related to memory dysfunction⁷³ and show experience-dependent improvements after memory training^{31,78}.

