Participants will be asked to keep still during the entire scan to minimize motion artifacts. During resting state recording, participants will be asked to close their eyes, relax their body and mind, but not to fall asleep or focus on any specific thought. Total Interdependence (TI; developed by Co-I [name]), will be used to quantify the functional connectivity between pairs of ROIs. Compared with Cross Correlation (CC), which exploits the covariance structures of zero-lag data but ignores temporal relations that extend beyond zero-lag, TI estimates the total amount of mutual information between the two extracted BOLD time series⁷⁹. The statistical treatment of TI is similar to that applied CC estimates, but it has been shown that, by revealing additional temporal relationships not captured by CC, TI reproduces more precise task activated networks, and provides greater sensitivity in correctly deciding network membership⁷⁹.

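### Objective 3.1 names cross correlation and total interdependence as primary connectivity measures, but only total interdependence, which has no sign, is carried into the analysis, so the direction of between-network coupling is not assessed

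*SAP*

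**What the plan says.** Protocol section 5, Aim 3, Objective 3.1, lists among its primary measures "functional connectivity (cross correlation and total interdependence) in identified brain networks damaged in TBI". That is two functional measures, both primary.

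Protocol 6.3.2.3.3 (Resting-State Functional MRI) is narrower. It says that TI "will be used to quantify the functional connectivity between pairs of ROIs". CC appears there only as the comparator, a method "which exploits the covariance structures of zero-lag data but ignores temporal relations that extend beyond zero-lag". The section describes TI in these words: "TI estimates the total amount of mutual information between the two extracted BOLD time series".

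SAP 2.6 follows that section. The imaging variables for the one-way ANOVA across the Encoding, Consolidation and Retrieval groups, with Tukey HSD follow-up, are "neuroimaging data (NEW, FA, diffusivity measures, morphological volumes, TI from RS-fMRI for specific ROI pairs". Neither CC nor any other signed connectivity measure is listed. The SAP's later remark about exploring additional measures concerns the Phase 3 treatment comparisons, not imaging.

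On rationale, 6.3.2.3.3 reports a suggestion in the literature "that TBI disrupts the normal segregation of" (the sentence is split by Table 3) "the DMN and TPN through white matter damage to large corticortical pathways", and links such abnormalities to memory dysfunction.

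**The concern.** There are two linked problems. The first is consistency: one of the two functional measures that Objective 3.1 calls primary has no planned analysis.

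The second is what the remaining measure can show. Mutual information measures how much two series depend on each other, not whether they move together or in opposition. For connections within a network, where coupling is expected to be positive, little is lost. For connections between networks the sign can be the point of interest: the protocol describes the DMN as deactivating during tasks and the TPN as becoming more active, and it cites their segregation as something that TBI may disturb. If such pairs are analysed with TI alone, a lower value in one subgroup could mean weaker opposition or weaker positive coupling, and a difference in sign at equal strength would not appear. A functional signature of the kind Objective 3.1 seeks could be missed or described in the wrong direction.

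**Working it through.** **No figure to reproduce.** The documents give no power, effect size or sample size for the imaging analysis. The check compares the texts, then works out what TI does with sign.

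**Texts side by side**

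| Place | Functional-connectivity measures |
|---|---|
| Protocol, Objective 3.1 | CC and TI, both primary |
| Protocol 6.3.2.3.3 | TI; CC only as comparator |
| SAP 2.6 | TI only |

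The conflict is between Objective 3.1 and the two later texts.

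**Sign.** Multiplying one series by -1 leaves mutual information unchanged, at every lag and without a Gaussian assumption. The zero-lag Gaussian case illustrates this:

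- Mutual information = -0.5 × ln(1 - r²). At r = -0.3 and at r = +0.3 it is -0.5 × ln(0.91) = 0.047. At r = 0 it is 0.
- Fisher z = atanh(r), so the same two groups differ by 2 × atanh(0.3) = 0.62.

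**Illustrative detection rates, two groups.** Inputs from the documents: 8 min 10 s at TR 2.5 s gives 490 / 2.5 = 196 volumes (Table 3), and 4 participants per classification group (protocol 6.4.2, stated for Phase 3). Assumptions not in the documents: the true correlations, the between-person SD on the z scale, and two-sided alpha 0.05. Method: 4 versus 4 t-tests on Fisher z and on zero-lag mutual information.

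| True r in the two groups | Assumed SD | CC | TI |
|---|---|---|---|
| -0.3 v +0.3 | 0.1 | about 100% | 3-4% |
| -0.3 v +0.3 | 0.2 | about 92% | about 4% |
| -0.3 v +0.3 | 0.3 | about 66% | 3-4% |
| -0.3 v +0.3 | 0.4 | about 44% | not tabulated |
| -0.3 v 0 | 0.1 | about 84% | about 54% |
| -0.3 v 0 | 0.2 | about 40% | about 13% |
| -0.3 v 0 | 0.3 | about 23% | about 6% |
| -0.3 v 0 | 0.4 | about 15% | about 4% |
| +0.5 v +0.2 | 0.2 | about 49% | about 41% |

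TI's rate for the opposite-sign case is no more than the nominal false-positive rate. For the two positive correlations TI gives up little.

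**The planned three-group ANOVA.** This run used 3 groups of 4, TI computed from coherence so that lagged relations count, an assumed AR(1) coefficient of 0.4, SD 0.2 and 800 runs.

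| True r in the three groups | ANOVA rejects, CC | ANOVA rejects, TI | Mean TI by group |
|---|---|---|---|
| -0.3, -0.3, +0.3 | 0.96 | 0.05 | 0.242, 0.238, 0.241 |
| -0.4, -0.4, 0 | 0.64 | 0.23 | 0.316, 0.315, 0.147 |
| +0.4, +0.4, 0 | 0.67 | 0.24 | 0.315, 0.321, 0.148 |

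The last two rows show the ambiguity. Lost opposition and lost positive coupling give the same fall in TI, from about 0.32 to 0.15.

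**The case against.** The strongest case on the other side has five parts.

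- **TI was chosen for a reason.** Protocol 6.3.2.3.3 argues that TI captures relations beyond zero lag and decides network membership more sensitively. That stands as a reason to keep TI. It does not address direction, so it is no reason to leave CC out.
- **The SAP did not remove CC.** A reader might infer that it did. The TI-only choice is already in the protocol's methods section, and the SAP follows it. This stands: both places need attention.
- **Loss of segregation is not testable here in any case.** A reader might infer that using TI alone is what prevents loss of DMN-TPN segregation from being identified. The documents do not support that. Segregation is offered as a suggestion from the literature, not as a hypothesis or endpoint, and no reversal of sign is described. The ANOVA compares three TBI subgroups, and no uninjured imaging group is described. Even with CC it would test differences between subgroups, not departure from normal.
- **The problem may touch few pairs.** The ROI pairs are not listed, and the first-named focus is inferior frontal to medial temporal connections. DMN-TPN may not be among them. This stands, and limits the point to between-network pairs that are actually analysed.
- **The large contrast in detection rates rests on a chosen case.** It assumes opposite signs in two TBI subgroups, and it uses the Phase 3 group size because no Phase 2 imaging sample size is given. At SD 0.1, TI detects the -0.3 v 0 difference in over half of runs. The rates are therefore illustrations only. The loss of sign depends on none of these assumptions.

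**Conclusion.** The point holds in a limited form. A measure that Objective 3.1 names as primary has no planned analysis, and the measure that remains cannot give direction. For between-network pairs, a TI difference shows that strength of dependence differs between subgroups but not whether the networks are opposed or coupled, and equal-strength coupling of opposite sign is invisible to it. TI remains able to detect differences in strength.

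The sign argument needs only the protocol's own description of TI as mutual information. The size of the practical loss depends on which ROI pairs are chosen, on the true correlations and on the between-person SD, none of which the documents give. It ranges from slight, where all coupling is positive, to complete, where groups differ only in sign. This is a modest but worthwhile correction: the missing measure is already promised and comes from data already planned.

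**What to change.** In SAP 2.6, and to match in protocol 6.3.2.3.3, add Fisher-z cross correlation beside TI for the same ROI pairs, as Objective 3.1 states. Specify that direction is taken from CC and strength from TI, and that a TI difference is not read as gain or loss of connectivity without the sign of CC.

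The alternative that would also reconcile the texts is to remove CC from Objective 3.1 and state that direction of coupling will not be assessed. That is consistent but gives up information that is available at almost no cost.

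Cost of the preferred change: a short text edit in each document and one further computation on the same extracted BOLD series, with no new scans. The downside is one more measure per ROI pair, which adds to the number of tests.
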